The goal of this Fast-Track STTR project is to optimize and test a novel arm restraint in older critically ill mechanically ventilated patients that increases mobility; reduces agitation, use of sedative medications, and delirium; and exhibits high satisfaction and acceptability among hospital staff, family members, and patients. Older mechanically ventilated patients are often immobilized with wrist restraints to prevent self-extubation and are sedated to reduce agitation caused by their restraints and endotracheal (breathing) tube. This sedation and immobility lead to complications, including delirium and muscle weakness, that are independently associated with long term cognitive impairment, reduced physical functioning, and mortality. Specifically, the incidence and duration of delirium in the ICU are strongly and independently associated with long-term cognitive impairment that is similar to Alzheimer's Disease and Related Dementias.

Healthy Design is developing the novel *Exersides*TM restraint that allows arm mobility but prohibits hands from reaching oral/nasal endotracheal and feeding tubes or intravenous lines. Because it permits mobility, *Exersides*TM may reduce agitation and the need for sedatives. In preliminary pilot testing, *Exersides*TM has demonstrated very encouraging results. The objectives of this STTR Fast-Track project are to optimize *Exersides*TM and evaluate it in a randomized controlled trial (RCT) in older critically ill patients at high risk for delirium and associated long-term cognitive impairment. The multidisciplinary investigator team has expertise in critical care, extensive experience in conducting ICU RCTs, and a history of successful collaboration.

During Phase I, a prospective study will be performed in 8 older mechanically ventilated patients to demonstrate that 1) the revised *Exersides*TM prototype is safe and 2) the RCT proposed in Phase II is feasible. The milestones to proceed to Phase II are to demonstrate that: 1) the revised *Exersides*TM restraint has mean incidence rate <5% across 7 pre-specified safety criteria in mechanically ventilated

older patients who require restraint; and 2) the RCT in phase II is feasible by successfully enrolling 8 ICU patients into the phase I study and completing at least 90% of all proposed outcome measures.

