

18 Patton MQ. Qualitative Research & Evaluation Methods: Integrating Theory and Practice. 4th ed. Thousand Oaks, CA: Sage Publications, 2015;

20 Nalamalapu SR, [name] DM, [name] RD. Patient Recruitment Rate in Multicentered Randomized Trials in Critical Care. *Crit Care Med* 2016; 44:e588-589

Objectives: Clearly state the primary and secondary objective(s) of the study.

Phase I Specific Aims:

1. To revise the *ExersidesTM* prototype based on feedback obtained from standardized patients in the UVM simulation center.
2. To demonstrate that the revised *ExersidesTM* restraint is safe, and that conducting the proposed RCT (for STTR Phase II) is feasible, by performing a prospective evaluation in 8 mechanically ventilated older patients who require wrist restraint, including pilot testing all proposed measurements and outcomes planned for STTR Phase II

Milestones to progress to Phase II: (A) Demonstrate that the revised *ExersidesTM* prototype is safe in older mechanically ventilated patients who require restraint (i.e., has mean incidence <20% across pre-defined safety criteria, including: skin breakdown and laceration, reportable injuries to patients and clinicians, self-removal of the restraint, and damage to ICU bed or equipment), and (B) Demonstrate feasibility of the RCT planned for STTR Phase II, including enrollment of 8 ICU patients and completion of >90% of all outcomes/measures.

Phase II Specific Aims:

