3. To conduct a multi-site, within-patient crossover RCT in older mechanically ventilated patients requiring restraint to test the following **hypotheses** regarding *ExersidesTM* vs. traditional wrist restraints:
 - a. *ExersidesTM* allows greater upper extremity **activity**, as measured by actigraphy (primary outcome)
 - b. *ExersidesTM* reduces **delirium, agitation, and use of sedatives**, analgesics and antipsychotics
 - c. *ExersidesTM* has high satisfaction, assessed via both **quantitative and qualitative evaluations**, among ICU clinicians, families and patients.

METHODS AND PROCEDURES

Study Design, Procedures, and Statistical Analysis Plan (all included here for Phase I and then Phase II):

PHASE I (small cohort study to assess feasibility and safety)

Aim 1: To revise the *Exersides™* prototype based on pre-existing user feedback

- For this Aim, we and the company (Healthy Design, Ltd) will utilize the UVM Simulation Center to test the current device in 3 standardized patients. During this session, comfort, safety, and satisfaction will be evaluated in a simulated hospital setting. Following this session, any revision of the novel device needing to occur based on feedback obtained will be performed by the manufacturer before proceeding to Aim 2. Prevention of safety issues listed below in Aim 2 will be addressed during device refinements by surveying for sharp edges or hard protrusions and adding padding, as well as ensuring that securing straps are appropriately positioned, wide and padded.

Aim 2: To demonstrate safety of the *Exersides™* restraint and the feasibility of conducting an RCT (Aim 3, STTR Phase II) by performing a pilot cohort study to assess the restraint in 8 older ICU patients.

- Study Site:** UVM, a large regional hospital with extensive ICU RCT experience, is located close to Healthy Design, with Drs. [name] and [name] having a pre-existing collaborative working relationship.
- Patients (n=8):** We will conduct a study of 8 elderly ventilated ICU patients requiring restraint per an active physician order. See inclusion and exclusion criteria below in Table 4.

Table 4: Inclusion and Exclusion Criteria for Study Entry into STTR Phase I and Phase II Studies

Inclusion Criteria	Exclusion Criteria	Rationale for Exclusion
1. >60 years old	1. Upper extremity impairments that prevent use of novel restraint device (e.g. amputation, arm injury)	Unable to receive proposed intervention

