- Description of restraint intervention:** All 8 patients will wear both the *Exersides™* and traditional wrist restraint devices on both arms, sequentially, over 2 study days. On Day 1, they will wear the *Exersides™* restraint on both arms from 9am-1pm and wrist restraints on both arms from 1pm-5pm. On Day 2, they will wear the restraints on both arms in the opposite order. During each 4-hour period, subjects will be observed by research and nursing staff, with validated and reliable hourly assessments of sedation/agitation (RASS) status,¹ and validated and reliable delirium assessment (CAM-ICU) at the start and stop of each period (see Aim 3, Outcome 2 for description of RASS and CAM).¹ Subjects will wear actigraphs on both wrists to measure mobility/activity continuously. A digital video camera will be set up at the foot of the patient's bed to continuously record his/her movements during the study sessions. Overnight between Days 1 and 2, subjects will resume traditional restraints, per MD order. Intervention ends on Day 2. Satisfaction/acceptability/perceptions of device will be assessed in nurses, family members, physicians, and patients as per RCT protocol (see Aim 3, Outcome 3).
- Phase I Outcomes:**

1. Demonstrate that revised prototype is safe, with <20% mean incidence across 7 safety criteria in the 8 subjects enrolled. Safety criteria in STTR Phase I will include: 1) clinician or patient laceration (Grade 2b or higher, per STAR laceration grading criteria⁹) from any sharp edges of device, 2) development of pressure ulcer from device of Stage 3 or greater per 2016 National Pressure Ulcer Advisory Panel Pressure Injury Stages,¹⁰ 3) reportable injury (per local institutional standards) of patient by device, 4) reportable injury (per local institutional standards) to clinician by device, 5) self-removal of device, 6) damage to hospital bed rendering it non-functional, and 7) damage to ICU equipment (e.g. ventilator) rendering it non-functional..
2. Demonstrate that conducting the proposed RCT in Aim 3 is feasible, by consent/recruitment rate and pilot testing measures/outcomes for the RCT, via the following tasks:
 - **Consent/Recruitment:** 8 patients consented and enrolled within ≤ 7 months

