 - **Outcomes/measures:** At least 90% of all outcomes planned for the RCT in Aim 3 (STTR Phase II) will be measured in the 8 patients: 1) actigraphy counts, 2) RASS sedation/agitation score,¹ 3) CAM-ICU delirium score,¹ 4) medication use, 5) satisfaction/acceptability/perceptions of novel restraint. Incidence of self-extubation will also be reported in addition to the following measures of efficacy: 1) patient-reported satisfaction measures including comfortable, safe, effective, preferable and more humane; and 2) staff-reported satisfaction measures including easy to don/doff, easy to change level, safe for staff, effective, preferable and more humane. See Aim 3 for these RCT measures.

- **Data collection/management, quality assurance & analysis:** See Aim 3.
- **Sample size:** N=8 was based on feasible enrollment from the single study site during the 9-month Phase I period (i.e., ~1 patient/month). Literature suggests that there is no advantage to including more than 6-10 subjects per group in a Phase I study, and most chemotherapeutic phase I studies have N=3 per cohort.¹ Thus, N=8 is adequate for the proposed Aims to prepare for the RCT in Aim 3.
- **Phase I Study follow-up.** The engineer will prepare a report on the outcomes of all assessments based upon STTR Phase I, and will decide (in consultation with the project leadership team) which device improvements/modifications will be required before use of device in Aim 3 (STTR Phase II).

PHASE II (3-site RCT to compare the novel restraint to traditional wrist restraints)

[figure not shown]
Aim 3: To conduct a multi-site, within-patient randomized crossover trial in older critically ill mechanically ventilated patients who require restraint, to compare the *Exersides™* restraint vs. traditional wrist restraints.

Overview and Study Design Phase II. The objective of the Phase II project is to conduct an RCT to measure 3 outcomes:

1. Mobility/activity evaluated by actigraphy (primary outcome)
2. Agitation, delirium, medication use (sedative, analgesic, and antipsychotic), and incidence of self-extubation (secondary outcomes)
3. Satisfaction with, and acceptability/perceptions of, the device by patient, family, and clinicians (secondary outcomes)

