Risks/Benefits: Describe any potential or known risks. This includes physical, psychological, social, legal or other risks. Estimate the probability that given risk may occur, its severity and potential reversibility. If the study involves a placebo or washout period, the risks related to these must be addressed in both the protocol and consent. Describe the planned procedures for protecting against or minimizing potential risks and assess their likely effectiveness. Where appropriate, discuss plans for ensuring necessary medical or professional intervention in the event of adverse effects to the subjects. Discuss the potential benefits of the research to the subjects and others. Discuss why the risks to the subjects are reasonable in relation to the anticipated benefits to subjects and others. Discuss the importance of the knowledge gained or to be gained as a result of the proposed research and why the risks are reasonable in relation to the knowledge that reasonably may result. If there are no benefits state so.

RISKS TO HUMAN SUBJECTS

Human Subjects Involvement, Characteristics, and Design

This research includes 4 components where human subjects will be enrolled:

- (A) Testing the revised *Exersides*TM restraint device on 3 healthy subjects (STTR Phase I);
- (B) A prospective cohort study in 8 older critically ill patients (STTR Phase I) where feasibility of doing a larger RCT will be demonstrated;
- (C) A multi-site randomized controlled trial (RCT in STTR Phase II) in which 54 patients will be enrolled; and
- (D) Feedback from family members and from clinicians (e.g., nurses, and physicians) caring for patients enrolled into either the studies in (B) or (C), from above, about their satisfaction with, and perceptions of, the

*Exersides*TM restraint.

Potential Risks

There are potential risks for all participants regarding potential breach of confidentiality and invasion of privacy. If a critically ill patient regains decisional capacity and is approached about the study for re-consent (after a legal next of kin has already provided informed consent for the patient), he or she may experience stress and/or discomfort.

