2. Membership: We will convene 4 independent voting members (3 members will constitute a quorum) who are not study investigators, and have no financial, scientific, or other conflict of interest with the trial. All members will provide written documentation of competing interests. We will include expertise in the following fields: 2 members from key subject areas involved in the research (clinical experts in critical care medicine, mobility and/or delirium/cognitive impairment), 1 from biostatistics, and 1 from clinical investigation/ trials. The group will designate a chair and an executive secretary from the group membership; the chair will be responsible for overseeing meetings, developing agendas, generating reports, and being the contact person for the DSMB. Because committee members will likely be located at various sites, the committee meetings may be conducted by teleconference.
3. Organization: The group will meet during the course of the trial as follows
 - a. Meeting coordination: All meetings will occur in 3 parts:
 - i. An open meeting with principal investigators, project coordinators, and statistician to review accrual and outcomes as per below.
 - ii. A partially closed meeting with the DSMB and study statistician only to review the study outcomes per below.
 - iii. A closed session for DSMB members only to discuss oversight issues, emerging results, comments, and recommendations, which will be discussed until consensus among members. The chair would reserve the right to break a tie, if needed.
 - b. RCT in STTR Phase II
 - i. Initial meeting for RCT
 1. Protocol, consent, and data quality review: The DSMB will meet again before start of the RCT in Phase II. They will review data from Phase I. They will also review the entire IRB-approved RCT protocol with regard to participant safety, recruitment, randomization, intervention, data management, quality control, and statistical analysis. Additionally, they

will review the informed consent documents for applicability and readability, and standard operating procedures for data management and control.

2. Safety review: The DSMB will review information for recruitment, subject retention, protocol adherence, intervention effects, gender and minority inclusion, and participant safety. The DSMB will review, discuss, and approve the plan for identifying, assessing, and transmitting serious adverse event (SAE) and adverse (AE) information to the DSMB.

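### The device may be modified after the Phase I safety milestone is met, and the DSMB is not asked whether the Phase I result still covers the version used in the RCT

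*Combined protocol and SAP*

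**What the plan says.** The milestones under Objectives require a demonstration that the revised "prototype is safe in older mechanically ventilated patients who require restraint". Phase I Outcomes gives the operational form: "Demonstrate that revised prototype is safe, with <20% mean incidence across 7 safety criteria in the 8 subjects enrolled". The opening summary states the same milestone differently, as a device that "has mean incidence rate <5% across 7 pre-specified safety criteria".

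Under Aim 2, Phase I Study follow-up, the engineer reports on the Phase I assessments and, consulting project leadership, decides "which device improvements/modifications will be required before use of device in Aim 3".

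The Data Safety Monitoring Plan (3.b.i, initial meeting for the RCT) has the DSMB meet before the RCT starts. On the Phase I data it says: "They will review data from Phase I". The DSMB also reviews the full IRB-approved protocol, with the intervention among the named topics. It may recommend that the trial go ahead unchanged, go ahead with modifications, or stop on safety grounds.

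**The concern.** The milestone is evidence about one version of a device, and the plan allows that version to be altered after the evidence is complete. Nowhere does the plan require an altered device to be checked again, cleared by the DSMB, or recorded by version.

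The parts most likely to change are those that bear on the safety criteria. Aim 1 addresses safety through edges, protrusions, padding and strap position. Table 3 feedback on the first prototype concerned strap pressure, strap adjustment and grip size. The Phase I criteria include laceration, pressure ulcer and self-removal. A change meant to cure one problem could affect another, and the Phase I result would not show it. What is at stake is whether the safety result that opens Phase II describes the device that RCT patients wear.

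**Working it through.** The plan states no figure on this point, so the check is mainly one of sequence.

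**Order of events**

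1. Aim 1: simulation session, then any further revision by the manufacturer.
2. Aim 2: the resulting prototype is worn by 8 ICU patients and judged against 7 safety criteria.
3. Phase I Study follow-up: the engineer, with leadership consulted, decides on modifications.
4. Data Safety Monitoring Plan: the DSMB meets before the RCT. The plan does not say whether step 3 must be finished by then.
5. Aim 3: RCT.

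A revision at step 1 is followed by observed testing in patients at step 2. A revision at step 3 is followed by no required test.

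**What the DSMB would see at step 4.** The Phase I data come from the version before step 3. The protocol under review, as now written, refers to the RCT device by name and gives no version, so a change to a strap or padding need not appear in it. A list of device changes is not among the items put to the DSMB. Tables 5 and 6 do not include device version among the variables collected.

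**Patient evidence tied to the tested version.** Each Phase I patient wears the novel device for 4 h on each of 2 days: 8 patients × 8 h = 64 h. For a version modified at step 3, the plan requires 0 patients and 0 h before the RCT.

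**Can the milestone be met while events occur that would prompt a redesign?** Assume each criterion counts at most once per patient and the 7 criteria are averaged equally. There are then 8 × 7 = 56 patient-criterion cells.

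| Threshold | Most events that pass | Next count, which fails |
|---|---|---|
| <20% (Objectives; Phase I Outcomes) | 11/56 = 19.6% | 12/56 = 21.4% |
| <5% (opening summary) | 2/56 = 3.6% | 3/56 = 5.4% |

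Under either threshold the milestone can be met with device-related events on record, so meeting it does not make a later modification unlikely. The two thresholds conflict and must be reconciled, because they decide what meeting the milestone means.

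**The case against.** The strongest reply is that independent review already stands between Phase I and the RCT. The DSMB sees the Phase I data and the whole protocol, can recommend modifications or stopping, and nothing prevents it from asking about the device. The engineer does not act alone. The modifications are those judged necessary, and optimising the device is the project's stated aim. The documents describe the device as Class I, exempt from 510(k) and IDE requirements, and of non-significant risk. All of this stands. It rules out any reading that a modified device would enter the RCT without independent review. What remains is narrower: the review is not directed at device changes, and the Phase I data before it may concern a different version.

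A reader might also infer that harm from a modified device would go unseen until the interim meeting after 27 patients. The documents do not support that. Events of interest are collected daily, related adverse events and unexpected serious ones go to the principal investigators within 24 hours, and unexpected related serious events go to the DSMB within 3 working days of the site's report. Ad hoc DSMB meetings are possible, and the DSMB may restrict or cease enrollment. Routine expedited reporting to the DSMB does not cover non-serious events, but monitoring is continuous.

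Nor does the same gap exist at Aim 1. There, "any revision of the novel device needing to occur based on feedback obtained will be performed by the manufacturer before proceeding to Aim 2", and Aim 2 then tests that version for safety in patients. At most the wording needs reconciling: Aim 1 has the volunteers test the current device with revision afterwards, while the human-subjects and benefits sections say they test the revised device. The Aim 1 heading refers to feedback already in hand, so the current device may already be a revised one.

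Finally, with 0 events in 8 patients the one-sided 95% upper bound for any single harm is 1 − 0.05^(1/8) = 31.2%. That reflects the Phase I sample size and applies equally to an unmodified device, so it is no evidence of a version problem.

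**Conclusion.** The point holds as a gap in the plan: the device used in the RCT need not be the version that met the safety milestone, and no one independent of the project is asked to decide whether the Phase I result still applies. If a change relevant to the safety criteria is made, the 64 h of Phase I wear in 8 patients becomes indirect evidence for the RCT device.

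The consequence is confined to what Phase I can say about safety. A reader might infer that the RCT's estimate is compromised; it is not. The comparison is randomised and within-patient, and the sample-size assumptions are described as informed by preliminary data, which the plan reports from an earlier actigraphy study. A change made before the RCT alters which device is evaluated, not the validity of the comparison. Changes during the RCT are not at issue either, since the plan places modification before Aim 3.

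The conclusion rests on the absence of any re-check, clearance or version-recording rule in the documents. It does not assume that a change was made or that one would be harmful. The event counts shown rest on the stated counting assumption and serve as context only.

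**What to change.** In Phase I Study follow-up and in Data Safety Monitoring Plan 3.b.i, state that:

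- an itemised list of all device changes made or planned since Phase I goes to the DSMB at its already planned pre-RCT meeting, so the list must be settled by then;
- before first RCT use, the DSMB, not the engineer alone, rules whether the Phase I safety result still applies to the version to be used or whether further checking is needed;
- the device version is recorded for each RCT patient.

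The cost is one agenda item, one data field, and a possible short delay if a relevant change is made. There is no need to default to the Phase I version, which could hold up correction of a defect that Phase I reveals, or to mandate a repeat volunteer session. The DSMB can decide what checking a given change warrants.

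In the same edit, reconcile the two milestone thresholds, and the wording on which version the Aim 1 volunteers test.
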